A follow-up visit approximately 28 days after last dose is required for all randomized patients, including those discharged from hospital before Day 14. Another follow-up visit occurs at approximately Study Day 60. These follow-up visits can be conducted as telephone visits.

Discharge from the hospital prior to Day 14 is not considered early discontinuation from the study drug or from the study. All randomized patients, including patients meeting criteria for early discontinuation of study drug, as specified in Section 7.1, should be encouraged to remain in the study for the scheduled study assessments specified in the Schedule of Activities (SoA) (Section 1.3). Patients who prematurely discontinue from the study should have an ETV and follow-up visits, if possible, as shown in the SoA.

The study schema is presented in Section 1.2.

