## COVID-19 pulmonary infection-related inclusion criteria

- [3] Hospitalized with coronavirus (SARS-CoV-2) infection, confirmed by polymerase chain reaction (PCR) test or other commercial or public health assay in any specimen, as documented by either of the following:
  - PCR positive in sample collected <72 hours prior to randomization; OR
  - PCR positive in sample collected ≥72 hours prior to randomization (but no more than 14 days prior to randomization), documented inability to obtain a repeat sample (for example, due to lack of testing supplies, limited testing capacity, results taking >24 hours, etc.) AND progressive disease suggestive of ongoing SARS-CoV-2 infection
- [4] Require supplemental oxygen at the time of study entry and at randomization.
- [5] Have indicators of risk of progression: at least 1 inflammatory markers >ULN (CRP, D-dimer, LDH, ferritin) with at least 1 instance of elevation >ULN within 2 days before study entry.

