#### Amendment D (20 October 2020):

This amendment is considered to be substantial based on the criteria set forth in Article 10(a) of Directive 2001/20/EC of the European Parliament and the Council of the European Union.

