#### **Overall Rationale for the Amendment:**

The main purpose of this protocol amendment is to modify the study inclusion criteria and provide the opportunity for the sample size to be increased (sample size re-estimation) during an interim analysis. These changes are based on newly available data from the ACTT-2 study and on evolution in clinical management of the disease. In addition, based on regulatory feedback, a follow-up visit is added at Day 60.

Sections # and Name	Description of Change	Brief Rationale
1.1, Synopsis: Overall Design	Added a Day 60 assessment in the	To evaluate safety and efficacy at
	follow-up period and increased the	Day 60 for this patient population
	total maximum duration.	based on regulatory feedback.
1.1, Synopsis: Number of	Changed sample size to 1000	To increase sample size based on
Participants	patients. Added text for a sample size	ACTT-2 data and modeling
	re-estimation to potentially increase	assessments. Included a sample size
	the final sample size beyond 1000	re-estimation to maintain an
	patients.	adequately powered study.
1.2, Schema	Changed figure to include a Day 60	To add a Day 60 assessment based
	assessment.	on regulatory feedback.
1.3, Schedule of Activities	Added a column for Day 60	To add a Day 60 assessment based
	assessments.	on regulatory feedback.
	Added text clarifying the conduct of	To provide clarity on study visit
	various procedures.	procedures.
	Added visit windows for patients	To provide greater visit window
	discharged from hospital.	flexibility for patients who have
		been discharged from the hospital.
2.2, Background	Added citations for NIH and WHO	To reflect current NIH and WHO
	guidelines on use of corticosteroids.	guidelines.
3, Objectives and Endpoints	Added an exploratory objective for	To reflect addition of Day 60
	long-term (at least Day 60) clinical	assessment based on regulatory
	outcomes.	feedback.
4.1, Overall Design	Added a Day 60 assessment in the	Regulatory feedback, as stated for
	follow-up period and increased the	Section 1.1; see also rationale for
	total maximum duration; changed	Section 5.1.
	description of study population.	
4.2, Scientific Rationale for	Added a statement and a phrase about	Regulatory feedback, as stated for
Study Design	the Day 60 assessment.	Section 1.1

Sections # and Name	Description of Change	Brief Rationale
4.3, Justification for Dose	Added bold font format and	To clarify for investigators; these

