# Amendment A (27 May 2020):

Amendment A occurred before any study participant was consented or dosed at any study site.

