**Table KHAA.6.9. Summary Tables Related to Adverse Events**

Analysis	Population or Analysis Set
An overview table, with the number and percentage of subjects who experienced a TEAE, serious adverse event, death, discontinued from study treatment due to an adverse event	Safety population
An overview table, with the number and percentage of subjects who experienced an event, serious adverse event, death, discontinued from study due to an adverse event	Follow-up analysis set
The number and percentage of subjects with TEAEs using MedDRA Preferred Term nested within System Organ Class	
The number and percentage of subjects with FEAEs using MedDRA Preferred Term nested within System Organ Class	Follow-up analysis set
The number and percentage of subjects with TEAEs using MedDRA Preferred Term	Safety population
The number and percentage of subjects with TEAEs by maximum severity using MedDRA Preferred Term	Safety population
The number and percentage of subjects with TEAEs using MedDRA Preferred Term for the common TEAEs (occurred in $\geq 2\%$ before rounding of treated subjects)	Safety population
The number and percentage of subjects who experienced a serious adverse event (including deaths and SAEs temporally associated or preceding deaths) using MedDRA Preferred Term nested within System Organ Class	Safety population
The number and percentage of subjects who experienced a serious adverse event (including deaths and SAEs temporally associated or preceding deaths) using MedDRA Preferred Term nested within System Organ Class	Follow-up analysis set
Listing of All SAEs	Safety population
The number and percentage of subjects who permanently discontinued from study treatment due to an adverse event (including adverse events that led to death) using MedDRA Preferred Term nested within System Organ Class	Safety population
Listing of AEs which led to permanent discontinuation from the study treatment and from the study	Safety population

Abbreviations: AEs = adverse events; ITT = Intent-to-Treat; MedDRA = Medical Dictionary for Regulatory Activities; SAE = serious adverse event; TEAE = treatment-emergent adverse event.

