#### 1.1) Additional analyses for the main study (Day 60)

The following table gives planned analyses for the main study using Day 60 data.

Variable	Population	Analysis Method	Time Point	Groups/Subgroups
Observed OS values at Day 60	ITT population with a baseline NIAID OS and a value at the Day 60 Visit	Descriptive statistics as described in Table KHAA.6.1 for categorical/discrete data.	At the Day 60 visit.	Overall and by baseline 
 
• OS 4, 5, 6 and 5, 6 combined.
 
• Corticosteroid status (see Section 6.1.4)
 
• Age group (<65, ≥65)
 

All-cause mortality:	Patients in the ITT population, excluding randomized patients who discontinued on the day of randomization and have no baseline or postbaseline OS data.	Time to death from all causes, all time on study. Event dates are date of death for patients who died. Censor dates are last known information that indicates patient was alive. Patients who die after the visit window for Day 60, will be censored at the last date of their Day 60 visit window. KM curves and standard summary statistics (see Section 6.2.3 ) will be generated.	From baseline to end of study participation.	

Additionally, the following analyses will be performed after the Day 60 database lock for relevant subsets of the ITT population.

- Demographics
- Disposition
- Concomitant medications
- Safety analyses will include all adverse events occurring post primary outcome datalock up to an including Day 60. The following are the planned safety analyses:
  - Follow-up-emergent adverse events (FEAEs). FEAE is defined as an event that either first occurred or worsened in severity after Day 28 and on or prior to end of the study.
  - Serious adverse events
  - Adverse events leading to death
  - Overview of infections (includes herpes zoster, herpes simplex, opportunistic infections, and tuberculosis)

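### The Day 60 visit arrived with Amendment D, so follow-up after Day 28 is short and tied to dosing duration for patients who finished earlier, yet the Day 60 mortality and follow-up-event analyses do not separate the two groups

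*SAP*

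**What the plan says.** - **When the visit was added.** The amendment history (Protocol 10.6) states in the rationale for Amendment D, dated 20 October 2020, that "based on regulatory feedback, a follow-up visit is added at Day 60". The log also records a longer maximum study duration.
- **The other follow-up visit.** Protocol 4.1: "A follow-up visit approximately 28 days after last dose is required for all randomized patients, including those discharged from hospital before Day 14". The Schedule of Activities allows ±4 days. The Amendment D log lists no change to the timing of this visit.
- **Dosing.** Study drug stops at Day 14 or at discharge, whichever is earlier (Protocol 4.1).
- **Adverse event collection** ends at the last post-treatment follow-up visit (Protocol 8.3.1).
- **Day 60 mortality.** SAP Appendix 3, section 1.1, uses the ITT population less patients who left on the day of randomisation without any ordinal-scale data. It covers the whole of study participation, and "Censor dates are last known information that indicates patient was alive".
- **Follow-up events.** The same appendix counts events that begin or worsen after Day 28 up to the end of the study. SAP Table KHAA.6.9 plans "The number and percentage of subjects with FEAEs using MedDRA Preferred Term nested within System Organ Class" in the follow-up set, which SAP 6.1.1 defines without reference to protocol version.
- **Where a limit exists.** The Day 60 ordinal-scale summary is confined to patients with a value at that visit. The Day 60 safety analyses are to be run in subsets of the ITT population that the SAP does not define.

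**The concern.** Unequal follow-up from calendar time alone does no harm to a Kaplan-Meier curve. Here, though, the end of follow-up in the earlier patients is set by the day of last dose, which is usually the day of discharge. That is a post-randomisation outcome with prognostic content, and duration of hospitalisation is itself a key secondary endpoint. Two consequences follow.

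- **Crude percentages of follow-up events, SAEs and deaths** put a patient watched for 7 days after Day 28 and a patient watched for 32 days in the same denominator. The percentages are too low in absolute terms. The arm with fewer dosing days also has less time in which to record events.
- **The mortality curve beyond Day 28** loses the earlier patients in order of discharge. If those discharged early are at lower risk, the remaining risk set is too sick and the estimated level is too high.

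The Day 60 visit was added on regulatory feedback to evaluate safety and effectiveness (Protocol 4.2), and the plan has no longer follow-up. A reader will take these tables as the long-term evidence.

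**Working it through.** **1. Length of follow-up.** End of follow-up = max(last-dose day + 28, Day 60 if that visit applies). With the Day 60 visit: max(14 + 28, 60) = 60, which matches the stated duration of about 60 days. Without it, follow-up ends at Day d + 28, that is d days after Day 28, against 60 − 28 = 32.

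| Last dose (Day d) | Follow-up ends | Share of the 32 days, d/32 |
|---|---|---|
| 4 | Day 32 | 13% |
| 7 | Day 35 | 22% |
| 10 | Day 38 | 31% |
| 14 | Day 42 | 44% |

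With the ±4 day tolerance the earlier patients have 0 to 18 days after Day 28.

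**2. Share of earlier patients.** Not given. Assumed range: 20% to 60%.

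**3. Crude event percentages, absolute level.** Assume a constant rate with a 10% true risk over the 32 days and 8 dosing days. Rate = −ln(0.90)/32 per day. Earlier patients: 1 − exp(−8 × rate) = 2.6%. Pooled percentage = share × 2.6% + (1 − share) × 10%, which gives 8.5%, 7.0% and 5.6% at shares of 20%, 40% and 60%. With 5 to 12 dosing days the range is 5.0% to 8.8%.

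**4. Crude event percentages, between arms.** Assume a 5% true risk in both arms and mean dosing of 7 versus 9 days, with the mean used for every patient. Rate = −ln(0.95)/32. Earlier patients: 1 − exp(−7 × rate) = 1.12% and 1 − exp(−9 × rate) = 1.43%. Pooled with 5% for the later patients:

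| Earlier share | 7 days | 9 days | Ratio |
|---|---|---|---|
| 20% | 4.22% | 4.29% | 0.985 |
| 40% | 3.45% | 3.57% | 0.965 |
| 60% | 2.67% | 2.86% | 0.934 |

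**5. Kaplan-Meier level at Day 60.** Assume that 60% are discharged early, with last dose spread evenly over Days 2 to 8, and that 40% are dosed to Day 14. Day 28 mortality is 0.5% and 17% respectively; mortality over Days 29–60 among survivors is 0.3% and 6%, at a constant daily risk of 1 − (1 − 0.003)^(1/32) and 1 − (1 − 0.06)^(1/32).

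- Day 28 mortality: 0.6 × 0.5% + 0.4 × 17% = 7.1%.
- True Day 60 mortality: 7.1% + 0.6 × 0.995 × 0.3% + 0.4 × 0.83 × 6% = 9.27%.
- Kaplan-Meier: multiply survival at Day 28 by (1 − expected deaths / number at risk) for each of Days 29 to 60, removing earlier patients at d + 28. The results are 9.35%, 9.45%, 9.59% and 9.79% at shares of 20%, 40%, 60% and 80%, an excess of 0.08, 0.18, 0.32 and 0.52 points.
- If all earlier patients are censored at Day 28 instead, the result is 9.27% at every share.

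A second model gives the same order of size. It assumes daily hazards of 0.0005 if dosed under 14 days and 0.004 if dosed 14 days, and exponential dosing time with mean 8 days, capped at 14. Among patients alive at Day 28, simulated death by Day 60 was 3.69% against a true 3.59%, 3.91% against 3.65%, and 4.15% against 3.68%, at shares of 20%, 40% and 60%.

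**6. Between-arm mortality difference.** Use the model of step 5 with 60% versus 55% discharged early. The true difference is −1.06 points. Pooled Kaplan-Meier gives −1.06 at shares of 20%, 40% and 60%, and about −1.05 at 80%. Simulations of the same model moved the contrast by about 0.03 points or less.

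**The case against.** The strongest case against has several parts.

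- **The analyses are exploratory.** They lie outside the multiplicity scheme, and no Day 28 result depends on them. This stands, and it limits the weight of the point.
- **The size of the earlier group is unknown.** Patients still on study had to be re-consented to the current consent form (Protocol 10.1.3), so some could have a Day 60 visit, and last-known-alive information may extend some censor dates. This also stands. If the group is small, the effect is small.
- **The SAP does not state that it will pool for safety.** It leaves the subsets undefined, and the ordinal-scale row is already limited to patients with a Day 60 value. This is right: for the safety tables the defect is an undefined set and no patient-time measure. The mortality row does name its population, without an era limit.
- **Short dosing need not mean low risk.** Drug also stops for thromboembolism, laboratory abnormalities and other adverse events (Protocol 7.1.1), so the upward direction of the Kaplan-Meier error is an assumption.

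Three stronger readings should be resisted. A reader might infer that the mortality comparison is tilted towards baricitinib; step 6 does not show that. A reader might cite the ratio 1.12/1.43 = 0.78, but it belongs to the earlier patients alone, an analysis that nobody plans. And a reader might say the Day 60 row for patients without oxygen at baseline should go, because Amendment D made oxygen an entry requirement. No count supports that, and the row is descriptive and will show its n.

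**Conclusion.** The point holds as a worthwhile and cheap improvement to exploratory analyses. Patients who finished before Amendment D took effect at their site have about d of 32 days observed after Day 28, and the plan neither separates them nor adjusts for time observed.

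The crude event percentages are the more affected result. At an assumed 20% to 60% earlier share, a true 10% reads as 8.5% to 5.6%, and the between-arm ratio is 0.985 to 0.934 under no true difference with 7 versus 9 dosing days. The Kaplan-Meier level at Day 60 is too high by about 0.1 to 0.3 points (about 0.5 at 80%; up to about 0.5 at 60% under the second model), provided that early-discharged patients are at lower risk. The effect on the mortality contrast is negligible in the model examined. Event rates, dosing times and the earlier share are all assumptions; only the follow-up lengths come from the documents.

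**What to change.** In SAP Appendix 3 and Table KHAA.6.9:

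1. Report follow-up-emergent events, SAEs and deaths after Day 28 per patient-time observed, alongside the percentages.
2. Define the subset for the Day 60 safety analyses by randomisation date relative to the site's activation of Amendment D. One such rule is randomisation no more than 27 days before activation, so that activation falls on or before Study Day 28 and every included patient would still have been in follow-up whatever the dosing duration. Selecting patients by whether a Day 60 visit was actually scheduled would bring dosing duration back in, because at the transition only those with late last doses were still on study.
3. Add a Day 60 mortality sensitivity analysis that censors all other patients at Day 28. Show numbers at risk by era and list any deaths on Days 29–42 among the earlier patients.

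The Day 60 row for patients without oxygen at baseline can stay with its n.

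Cost: SAP wording, one derived flag and the site activation dates; no new data collection. A few observed deaths on Days 29–42 do not enter the sensitivity analysis, which is why they are listed. The planned Kaplan-Meier analysis still includes them.

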## 2) Addendum 5 Analyses (for Patients who are OS 7 at Baseline)

The following analyses are planned for randomized patients in Addendum 5 with baseline OS = 7. Patients who discontinue on the day of randomization with no baseline or postbaseline OS data will not be included.

1. NIAID-OS D4/7/10/14/28: overall improvement on the NIAID-OS evaluated at Day 4, Day 7, Day 10, 14 and Day 28
2. Proportion of patients with at least 1-point improvement on the NIAID-OS or live discharge from the hospital at Day 4, Day 7, Day 10, 14 and Day 28
3. Number of days alive and free of mechanical ventilation (VFD per main SAP), Day 1 to Day 28
4. Duration of hospitalization (Day 1 to Day 28)
5. Time to recovery (by Day 28)
6. All-cause mortality (Day 1 to Day 28).

Analyses 1-4 will use logistic regression with LOCF methodology. Analyses 5-6 will use time-to event methodology. All will follow the same methodology as the main SAP, except that treatment comparisons will be adjusted for baseline age group (<65, ≥65 years) and region rather than all the baseline stratification variables given in Section 6.1.4.

Patient disposition, patient characteristics and safety analyses will follow the main SAP to the extent possible (see Sections 6.7, 6.8, and 6.13).

The following table gives additional analyses for the Addendum 5 patients, utilizing their Day 60 data.

Variable	Population	Analysis Method	Time Point	Groups/Subgroups
Observed OS values at Day 60.	ITT population with a baseline NIAID OS and a value at the Day 60 Visit	Descriptive statistics.	At the Day 60 visit.	Overall (OS 7) 
 
• Baseline corticosteroid status (see Section 6.1.4)
 
• Age group (<65, ≥65)
 

All-cause mortality	ITT population with a baseline NIAID OS	Time to death from all causes, all time on study. Event dates are date of death for patients who died. Censor dates are last known information that indicates patient was alive. Patients who die after the visit window for Day 60, will be censored at the last date of their Day 60 visit window. KM curves and standard summary statistics (see Section 6.2.3) will be generated.	From baseline to end of study participation.	

Demographics, disposition, and safety analyses for Addendum 5 patients will mirror the main study to the extent possible. The main comparative safety analyses will be based on data from baseline to Day 28. There will be separate analyses of FEAEs, as described in Section 6.13.

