**Table KHAA.6.4. Description and Derivation of Primary, Key Secondary, and Associated Supportive Analyses**

Measure	Description	Variable	Derivation / Comment	Definition of Missing
NIAID-OS	Using data from the COVID-19 Clinical Status Assessment, results will be calculated for ordinal scales currently being used in other studies, and in this study, to measure clinical outcomes in patients treated for COVID-19, in particular the NIAID-OS. The NIAID-OS is as follows:	Patients who die or progress to requiring ventilation	Proportion of patients who progress to ventilation or death. In order to be counted as having this event: 
 
• Patients who start at OS 4 or 5 must progress to at least OS 6.
 
• Patients who start at OS 6 must progress to at least OS 7.
 
	Missing if NIAID-OS is missing and the variable status cannot be identified using remaining data.
	1. Not hospitalized, no limitations on activities	Ventilator-free days (days free of invasive mechanical ventilation)	Total number of days patients are alive and have a NIAID-OS less than 7	Missing if patient's NIAID-OS is missing for any day.
	2. Not hospitalized, limitation on activities and/or requiring home oxygen	1-point improvement in OS (at days 4, 7, 10 and 14)	Proportion of patients with baseline NIAID-OS minus NIAID-OS $\geq 1$	Missing if either baseline NIAID-OS is missing or if the observed NIAID-OS is missing on the day of assessment of 1-point improvement
	3. Hospitalized, not requiring supplemental oxygen – no longer requires ongoing medical care: (This would include those kept in hospital for quarantine/infection control, awaiting bed in rehabilitation facility or homecare, etc.)	Time to recovery	Time to reach NIAID-OS 1, 2, or 3 for the first time. The date reached is the first full day that OS 1, 2, or 3 is the patient's maximum OS for the day.	Missing if NIAID-OS is missing and time to event of interest cannot be identified using remaining data
	4. Hospitalized, not requiring supplemental oxygen – requiring ongoing medical care (COVID-19 related or otherwise)	Overall improvement (at days 4, 7, 10, and 14)	NIAID OS	Missing if observed NIAID-OS is missing

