**Table KHAA.6.5. Description of Primary, Key Secondary, and Associated Supportive Analyses**

Measure	Variable	Population	Analysis Method	Time Point	Analysis Type
NIAID-OS	Proportion of patients who died or progressed to non-invasive ventilation or high-flow oxygen (OS $\geq$ 6)	ITT: Population 1 - all randomized patients	Logistic regression using MI	By Day 28	Primary analysis
		ITT: Population 2 – patients who, at baseline, require oxygen supplementation and are not receiving dexamethasone or other systemic corticosteroids for the primary study condition.	Logistic regression using MI	By Day 28	Primary analysis
		ITT	Logistic regression using LOCF	By Day 28	Supportive analysis
		ITT: Population 2	Logistic regression using LOCF	By Day 28	Supportive analysis
		Safety Population	Logistic regression using MI	By Day 28	Supportive Analysis
		ITT Population, excluding patients who die within 24 hours of baseline and have Do Not Resuscitate (DNR) or Do Not Intubate (DNI) orders	Logistic regression using MI	By Day 28	Sensitivity Analysis
		Ventilator free days (VFD)	ITT	ANOVA using MI	By Day 28
	Wilcoxon rank-sum test using LOCF			By Day 28	Supportive analysis
	Proportion of patients with 1-point improvement	ITT	Logistic regression using MI	Day 4, 7, 10, 14	Key secondary analysis
			Logistic regression using LOCF	Day 4, 7, 10, 14	Supportive analysis

Measure	Variable	Population	Analysis Method	Time Point	Analysis Type
	Time to recovery	ITT	Log-rank test using IETI	By Day 28	Key secondary analysis
			Cox proportional hazards model using IETI	By Day 28	Supportive analysis
			Max-combo test using IETI (if needed)	By Day 28	Supportive analysis
NIAID-OS	Overall improvement	ITT	Proportional odds model using MI	Day 4, 7, 10, 14	Key secondary analysis
			Proportional odds model using LOCF	Day 4, 7, 10, 14	Supportive analysis
	Duration of hospitalization	ITT	ANOVA using MI	By Day 28	Key secondary analysis
			Wilcoxon rank-sum test LOCF	By Day 28	Supportive analysis
	All-cause mortality	ITT	Log-rank test	By Day 28	Key secondary analysis
			Cox proportional hazards model	By Day 28	Supportive analysis
Safety					
			Log-rank test	By Day 28	Supportive analysis
			Cox proportional hazards model	By Day 28	Supportive analysis
Oxygen Saturation	Proportion of patients with change in oxygen saturation from <94% at baseline to $\geq$ 94% at the observed time point	ITT	Logistic regression using LOCF	Day 4, 7, 10, 14	Key secondary analysis

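### SAP Appendix 3 assigns logistic regression to two day-count outcomes in the Addendum 5 patients, against the main SAP methods that the same paragraph says it follows.

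*SAP*

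**What the plan says.** The relevant text is in SAP Appendix 3, part 2 (Addendum 5 Analyses). It introduces its list with "The following analyses are planned for randomized patients in Addendum 5 with baseline OS = 7". OS 7 is invasive mechanical ventilation or ECMO. The first four entries are overall improvement on the NIAID-OS, the proportion who improve by a point or are discharged alive, "Number of days alive and free of mechanical ventilation (VFD per main SAP), Day 1 to Day 28", and duration of hospitalization over Day 1 to Day 28. Entries 5 and 6 are time to recovery and all-cause mortality.

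The method statement is "Analyses 1-4 will use logistic regression with LOCF methodology". Entries 5 and 6 are assigned to time-to-event methods. The paragraph then says: "All will follow the same methodology as the main SAP, except that treatment comparisons will be adjusted for baseline age group" and region, in place of the full set of stratification variables. The covariate set is the only exception it states.

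**The concern.** Binary logistic regression needs a two-level outcome, and analyses 3 and 4 are numbers of days. Neither Appendix 3 nor the main SAP gives a rule for turning days into a binary outcome. The paragraph also promises main SAP methodology, and for these outcomes that is something else. A programmer who follows one statement breaks the other.

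What is at stake is the pre-specification of two exploratory efficacy analyses in patients ventilated at entry. The main SAP already has two methods for these outcomes, ANOVA and Wilcoxon. A third that cannot be run as written leaves open which one is reported as the main result.

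**Working it through.** No arithmetic applies. The check is whether the type of each endpoint matches the method assigned to it, and whether that method agrees with the main SAP.

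**Step 1: endpoint type.** SAP Table KHAA.6.4 derives ventilator-free days as "Total number of days patients are alive and have a NIAID-OS less than 7". It derives duration of hospitalization as the number of days at NIAID-OS 4 to 7, set to 28 days for a patient who dies by Day 28. Both are bounded counts of days.

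**Step 2: what the main SAP reserves logistic regression for.** Section 6.2.1 uses it for discrete or binary variables and reports odds ratios and proportions. Section 6.2.2 sends quantitative variables to ANOVA. Section 6.2.4 sends overall improvement on the ordinal scale to the proportional odds model. Section 6.2.5 sends endpoints counted in days to the Wilcoxon rank-sum test and names ventilator-free days as its example. Protocol Section 9.4.1 also names Wilcoxon for ventilator-free days.

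**Step 3: side by side.**

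| Addendum 5 analysis | Type | Appendix 3 | Main SAP | Result |
|---|---|---|---|---|
| 1. Overall NIAID-OS | Ordinal, 8 levels | Logistic, LOCF | Proportional odds, MI; LOCF supportive (Table KHAA.6.5) | Loose wording, reconcilable |
| 2. Improvement by a point or live discharge | Binary | Logistic, LOCF | Logistic, MI; LOCF supportive (Table KHAA.6.5) | Consistent |
| 3. Ventilator-free days | Day count | Logistic, LOCF | ANOVA, MI; Wilcoxon, LOCF supportive (Table KHAA.6.5); ANOVA, LOCF in subgroups (Table KHAA.6.12) | Conflict |
| 4. Duration of hospitalization | Day count | Logistic, LOCF | As for analysis 3 | Conflict |

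**Step 4: what exactly conflicts.** LOCF does not. The main SAP uses it for both day counts, for instance "Wilcoxon rank-sum test using LOCF" in Table KHAA.6.5. The conflict lies in the model.

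**Step 5: count.** Two of the four analyses in the sentence, and two of the six in the list, carry a method that the main SAP does not use for that endpoint.

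**The case against.** The strongest reply is that this is a drafting slip that resolves itself. Entry 3 points to the main SAP for its definition, the paragraph says main SAP methodology applies, and the main SAP has LOCF methods for both day counts. A sensible analyst would ignore the word logistic. One could add that a cumulative-logit model can be fitted to days without a cut-off, so even the literal wording is not impossible. The analyses are also exploratory.

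Much of this stands. A slip is the likeliest explanation, and the consequence is small. It does not remove the conflict, however. The SAP describes the proportional odds model in its own section and applies it only to the ordinal scale, so using it on days would be a new method and would still breach the promise of main SAP methodology. Setting the word aside leaves ANOVA and Wilcoxon, with no statement of which leads.

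A reader might infer four stronger things that the documents do not support:

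- **That analysis 1 is also contradicted.** The proportional odds model is ordinal logistic regression and reports an odds ratio, so the wording there is imprecise but not wrong.
- **That days will be split at a cut-off chosen after the data are seen.** No cut-off or dichotomization is mentioned. SAP Section 3 says that Version 4, which added Appendix 3, was approved before the study team was unblinded for the primary outcome lock.
- **That the loss of precision can be quantified.** The textbook figure for a median split of a normal outcome (2/π, about 64% of the information kept) describes an analysis nobody planned, on outcomes bounded at 28 days and with deaths set to 28 hospital days.
- **That this is the smallest group.** Neither document gives a sample size for Addendum 5.

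**Conclusion.** The point holds for analyses 3 and 4. The method stated for ventilator-free days and duration of hospitalization does not fit day counts, and it conflicts with the commitment to main SAP methodology in the same paragraph. For analysis 1 only the wording needs tidying.

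The consequence is minor. SAP Section 4.3 and Appendix 3 place these analyses among the exploratory ones, and the testing scheme in Section 6.6 covers only the primary and key secondary endpoints. The trial's primary and key secondary conclusions are unaffected. The conclusion assumes that logistic regression in Appendix 3 carries the meaning given in SAP Section 6.2.1. Addendum 5 itself is not among the documents reviewed, so whether it names methods of its own could not be checked.

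**What to change.** Replace the method sentence in Appendix 3 with wording such as: *Analysis 1 will use the proportional odds model, analysis 2 logistic regression, and analyses 3 and 4 ANOVA adjusted for age group and region, with the unadjusted Wilcoxon rank-sum test as supportive; all with LOCF.*

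ANOVA comes first for two reasons. It can carry the age-group and region adjustment that Appendix 3 requires, which the Wilcoxon test of Section 6.2.5 cannot. It also keeps the order of Table KHAA.6.5, where Wilcoxon is supportive, and Table KHAA.6.12 already pairs ANOVA with LOCF for these two outcomes. Section 6.2.5 and Protocol Section 9.4.1 do favour Wilcoxon for ventilator-free days. If the sponsor prefers it as the lead method, the text should say that this comparison is unadjusted.

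The cost is one sentence, with no new data and no change to any other analysis.
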